8.2.2. Overall Survival

OS is defined as the time interval between the date of randomization and date of death from any cause. Patients who are still alive or are lost to follow-up will be censored at the date of last contact.

OS (months) = [date of death or censoring - date of randomization + 1]/30.4375

Analysis for OS in AP ITT Population will be stratified by the randomization stratification factors per IRT (mutation status [KIT exon 9 vs. KIT exon 11 vs. KIT/PDGFRA WT vs. other KIT {absence of exon 9 or 11}/PDGFRA] and intolerance to imatinib [yes vs. no]). Analysis for OS in Ex11 ITT population will be stratified by intolerance to imatinib per IRT [yes vs. no]. The p-value will be from a 2-sided stratified Log-rank test at 0.05 significance level for evaluation of treatment difference. Point estimate of hazard ratio will be obtained from a Cox proportional-hazards regression model stratified by randomization stratification factors per IRT; the associated 95% CI will be obtained using Wald method. OS will be summarized via KM methodology using the 25th, 50th (median), and 75th percentiles and survival probability at prespecified timepoints, each with associated 2-sided 95% confidence intervals. The estimated survival functions will be displayed in a KM plot.

8.3. Analysis of Other Secondary Efficacy Endpoints

All other secondary efficacy endpoints will be analyzed for Ex11 ITT and AP ITT populations. The secondary endpoints of DOR, TTR, TTP will be analyzed based on both IRR and INV. PFS based on INV will be analyzed as other secondary efficacy endpoints.

CONFIDENTIAL Page 18 of 29

8.3.1. Duration of Response

DOR is defined, for patients with objective response (confirmed CR or confirmed PR), as the time interval from the first assessment of CR or PR, which is subsequently confirmed, until the first assessment of disease progression or death, whichever occurs first. The censoring rules for DOR are the same as those for PFS.

DOR (months) = [date of event or censoring–first date of objective response +1]/30.4375

DOR will be analyzed with Kaplan-Meier method using the 25th, 50th (median), and 75th percentiles and survival probability at pre-specified timepoints, each with associated 2-sided 95% confidence intervals. Comparison of DOR between the two arms and estimation of HR will be done in a similar fashion as for PFS.

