The p-value from a 2-sided stratified log-rank test at 0.05 significance level will be used for evaluation of treatment difference. Point estimate of hazard ratio will be obtained from a Cox proportional-hazards regression model stratified by randomization stratification factors per IRT and the associated 95% CI will be obtained using Wald method. PFS time will be summarized via Kaplan-Meier (KM) methodology using the percentiles (25th, 50th [median], and 75th), survival probabilities at pre-specified timepoints with associated 2-sided 95% confidence intervals, and KM plot of the estimated survival functions.

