8.2.1. Objective Response Rate

Best overall response (BOR) will be assessed based on reported overall tumor responses at different evaluation timepoints from the date of randomization until the first documentation of

CONFIDENTIAL Page 16 of 29

disease progression, death, surgical resection on GIST lesions or radiotherapy of GIST lesions, or start of new anticancer therapy, whichever occurs first.

BOR Based on Confirmed Responses:

- Confirmed Complete Response (CR): at least two determinations of CR at least 4 weeks apart (allowing a minus 3-day window) and before first documentation of disease progression
- Confirmed Partial Response (PR): at least two determinations of PR or better (PR followed by PR or PR followed by CR) at least 4 weeks apart (allowing a minus 3-day window) and before first documentation of disease progression (and not qualifying for a CR)
- Stable Disease (SD): at least one SD assessment (or better) ≥ 6 weeks (allowing a minus 3-day window) after the date of randomization and before first documentation of PD (and not qualifying for confirmed CR or confirmed PR).
 - Non-CR/non-PD per IRR review will be reported together as SD (applicable only to patients without target lesions at baseline per IRR): at least one non-CR/non-PD assessment (or better) ≥ 6 weeks (allowing a minus 3-day window) after the date of randomization and before first documentation of PD (and not qualifying for confirmed CR or confirmed PR).
- Progressive Disease (PD): first documentation of PD ≤ 14 weeks after the date of randomization (and not qualifying for confirmed CR, confirmed PR, or SD).
- Not evaluable (NE): all other cases.
 - Undefined per IRR review will be reported together as NE (applicable only to patients with neither target lesions nor non-target lesions at baseline per IRR)

Objective response is defined as BOR of either a confirmed CR or a confirmed PR. ORR is defined as the proportion of patients with a confirmed CR or a confirmed PR as the BOR. Patients with non-evaluable or missing response will be treated as non-responders and will be included in the denominator during calculation.

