8.5. Multiple Comparisons/Multiplicity

To control familywise type-I error at 0.05 level, the hypothesis tests for treatment difference will be performed according to the hierarchical testing sequence below:

- 1. PFS by IRR in Ex11 ITT (two-sided 0.05 level)
- 2. PFS by IRR in AP ITT (two-sided 0.05 level)
- 3. ORR by IRR in Ex11 ITT (two-sided 0.05 level)
- 4. ORR by IRR in AP ITT (two-sided 0.05 level)
- 5. OS in Ex11 ITT (two-sided 0.05 level)

CONFIDENTIAL Page 22 of 29

6. OS in AP ITT (two-sided 0.05 level)

The testing starts from PFS in Ex11 ITT and each subsequent endpoint will only be tested if all the testing preceding to it have been statistically significant. If the testing for any endpoint fails to meet statistical significance, the testing and p-value for all the subsequent endpoints will be nominal and statistical significance won't be claimed for all the subsequent endpoints.

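### SAP 8.3.1 tests duration of response between arms and estimates a hazard ratio in confirmed responders only, so the result is not a randomised comparison and can be biased when the arms differ in who responds

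*SAP*

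**What the plan says.** SAP 8.3.1 restricts the endpoint to responders: "DOR is defined, for patients with objective response (confirmed CR or confirmed PR), as the time interval" from the first response that is later confirmed to progression or death. The clock starts at response, not at randomisation: "DOR (months) = [date of event or censoring–first date of objective response +1]/30.4375". Kaplan-Meier summaries follow, and then: "Comparison of DOR between the two arms and estimation of HR will be done in a similar fashion as for PFS".

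The PFS method is in SAP 8.1.1: "The p-value from a 2-sided stratified log-rank test at 0.05 significance level will be used for evaluation of treatment difference", with a hazard ratio from a stratified Cox model and a Wald 95% CI. SAP 8.3.1 gives no significance level of its own for DOR and does not call the comparison descriptive.

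SAP 8.3 applies the other secondary endpoints to both the Ex11 ITT and AP ITT populations and adds: "The secondary endpoints of DOR, TTR, TTP will be analyzed based on both IRR and INV". The multiplicity rule in SAP 8.5 says that "the hypothesis tests for treatment difference will be performed according to the hierarchical testing sequence below". That sequence covers PFS, ORR and OS, each in two populations. DOR is not in it.

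The list of other secondary endpoints in protocol 9.2.2.2 does not contain DOR, so SAP 8.3.1 is the only plan for it.

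**The concern.** Whether a patient responds is itself an outcome of treatment. Randomisation makes the full ITT sets comparable. It does not make the responders within them comparable. If one drug brings more patients into response, it may admit patients with shorter disease control whom the other drug would have left as non-responders. The log-rank p-value and the hazard ratio then mix how long responses last with which patients responded.

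Printed beside the PFS result, a DOR hazard ratio would naturally be read as a treatment effect. The arm whose patients spend more time in response overall could look worse. What is at stake is a misleading nominal secondary result.

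**Working it through.** **1. The SAP's own contrasts.** Time to response (SAP 8.3.2) uses the same responder subset and is summarised descriptively only. ORR (SAP 8.2.1) keeps every patient: "Patients with non-evaluable or missing response will be treated as non-responders and will be included in the denominator during calculation". DOR combines the responder subset with a between-arm comparison. Number of comparisons: 2 populations x 2 assessors = 4.

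**2. Is there a planned figure to reproduce?** No. The documents give no event count, power or planning response rate for DOR, so the size can only be illustrated.

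**3. Inputs.**
- From the documents: 213 patients per arm; sunitinib median PFS 6 months, used for both arms; 21 months of accrual plus 8 of follow-up, so follow-up is uniform on 8 to 29 months (SAP 2.3); scans every 42 days at first, 42/30.4375 = 1.38 months (protocol Table 1); confirmation after at least 4 weeks (SAP 8.2.1).
- Borrowed: a response rate of 24%, the Phase 1, investigator-assessed, pooled second- and third-line figure (protocol 1.3.2.3 and 1.5.1).
- Assumed: a comparator response rate of 24%, 18%, 15% or 10%; response-PFS correlation of 0, 0.3 or 0.6; first response at 1.38, 2.76 or 4.14 months with probabilities 0.5, 0.3 and 0.2.

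**4. Model.** PFS is exponential and identical in both arms. Response is linked to PFS by a Gaussian copula, with the threshold set to give the stated response rate. The hazard ratio is for the arm listed first. Rejection is the share of 4,000 trials in which an unstratified log-rank test in responders gives two-sided p < 0.05. Its Monte Carlo standard error at 5% is sqrt(0.05 x 0.95/4000) = 0.3 points. Where a range is shown, it is the spread between repeated simulation runs.

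| Response rates | Correlation 0 | Correlation 0.3 | Correlation 0.6 |
|---|---|---|---|
| 24% v 24% | HR 1.00; 5.1% | HR 0.99; 5.1% | HR 0.99; 4.8% |
| 24% v 18% | HR 1.00; 4.6% | HR 1.02-1.05; 5.1% | HR 1.11-1.13; 7.0% |
| 24% v 15% | HR 1.00; 5.7% | HR 1.06-1.08; 5.7% | HR 1.22-1.23; 9.9% |
| 24% v 10% | HR 1.00; 5.4% | HR 1.12-1.15; 6.7% | HR 1.39-1.42; 15.3% |

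Reversing the response rates gives the reciprocals. Dropout of about 20% changes the rejection rates by less than 1 point.

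**5. Which arm really does better?** Take 24% v 18% at correlation 0.6. Mean time in response to month 18 among responders is 10.57 v 11.06 months, which favours the arm with fewer responders. Over all randomised patients, with non-responders counted as zero, it is 0.24 x 10.57 = 2.54 v 0.18 x 11.06 = 1.99 months, which favours the other arm.

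**6. A second model.** Here a latent prognostic factor drives both response and duration, and the drug has no effect on duration. At 24% v 10% the hazard ratio is 1.01 when response is unrelated to prognosis, 1.15 to 1.29 at correlation 0.5 to 0.8, and 0.85 at correlation -0.5. With the response rates reversed, the correlated cases give 0.86 to 0.77, and 1.16. So the bias can run either way.

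**7. Precision.** At 24% v 18% there are about 213 x (0.24 + 0.18) = 89 responders, and the simulation gives about 55 events at correlation 0.6. The 95% CI factor is exp(1.96/sqrt(55 x 0.57 x 0.43)) = 1.7 either way.

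**The case against.** The strongest reply is that this matters little. DOR is outside the SAP 8.5 hierarchy, and SAP 2.1.3 frames its objective as assessment, not comparison. At 24% v 18% the bias is small beside a confidence interval of a factor of 1.7 either way. All-randomised measures are already planned: PFS (SAP 8.1.1), ORR (8.2.1), DCR (8.3.4) and TTP (8.3.5). The DOR result would not stand alone. All of this stands, and it is why the severity is low.

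The sizes also depend on a comparator response rate and a correlation that the documents do not give. The 24% figure is not from independent review under mRECIST. That stands too: confidence belongs to the principle, not to any one number. The four comparisons are not four independent chances of a false finding, because Ex11 is nested in AP and both assessors read the same patients' scans.

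A reader might go further and judge the DOR hazard ratio against the planning PFS hazard ratio of 0.667, calling any difference bias. The documents do not support that. DOR has a different clock and need not share the PFS hazard ratio. With medians of 9 v 6 months and equal 24% response rates, the model gives a DOR hazard ratio of about 0.62 at correlation 0.3 and 0.54 at 0.6. Yet the ratio of median DOR is 1.51 and 1.56, essentially the time ratio of 9/6 = 1.5 built into the model. That shift mainly reflects the shape of responders' survival times and does not show selection bias.

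What the reply does not remove is the text itself: a between-arm comparison in a post-randomisation subset, with no caveat.

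**Conclusion.** The concern holds in a limited form. As written, SAP 8.3.1 yields a DOR p-value and hazard ratio that are not a randomised comparison and can be biased when the arms differ in who responds.

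Under identical PFS and correlation 0.3 to 0.6, the hazard ratio against the arm with more responders runs from about 1.02-1.05 up to 1.13 at 24% v 18%, and from about 1.12-1.15 up to 1.42 at 24% v 10%. There is no bias at zero correlation or, with identical PFS, at equal response rates. The rejection rates apply to trials of AP ITT size; Ex11 ITT was not simulated.

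A reader might infer that the trial's error control or main conclusion is at risk. It is not: the primary conclusion, power and familywise error are untouched. The harm is confined to nominal, mutually dependent secondary results.

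**What to change.** In SAP 8.3.1 keep the Kaplan-Meier DOR estimates with 95% CIs by arm and label them *descriptive, in confirmed responders only*, in line with the handling of time to response in SAP 8.3.2. Replace the comparison sentence with: *No between-arm test or hazard ratio will be reported for DOR.* If the sponsor wishes to keep the hazard ratio, report it without a p-value and label it as a non-randomised comparison.

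If a between-arm comparison is wanted, define it in all randomised patients of each ITT population. Use either the probability of being in response over time, or the mean duration of response to a fixed time with non-responders counted as zero.

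The cost is one sentence and one label, with no new data. The loss is a nominal p-value and an imprecise hazard ratio. The optional all-randomised measure needs one short paragraph and uses response, progression and death dates already collected.

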8.3.2. Time to Response

TTR is defined, for patients who achieved objective response, as the interval between the date of randomization and the first assessment date of CR or PR which is subsequently confirmed. Time to response will be summarized using descriptive statistics for confirmed responders only.

8.3.3. Quality of Life

Quality of life (QOL) will be based on European Organisation for Research and Treatment of Cancer Quality of Life Questionnaire for Cancer 30-item (EORTC-QLQ-C30), Dermatology Life Quality Index (DLQI), Question GP5 from Functional Assessment of Cancer Therapy-General (FACT-G) questionnaires and EuroQol Visual Analogue Scale (EQ-VAS).

8.3.3.1. EORTC QLQ C30

The questionnaire of EORTC QLQ-C30 is composed of multi-item and single-item scales. These include 5 functional scales, 9 symptom scales, and a global health status/QOL scale. The multi-item scale is scored at four levels from "not at all" (1), "a little" (2), "quite a bit" (3) and "very much" (4). Two single items assess the patient's global health status over the past week using self-reported scales with "very poor" (1) to "excellent" (7). The focus of the analysis will be on the physical function and role function scales plus the two global health status items.

The EORTC QLQ C30 will be summarized by scales per the manual. In all scales, a high scale score represents a higher response level. The scoring for this questionnaire will be done in 2 steps:

- Calculate the average of the items that contribute to the scale. This will be used as the raw score for the scale, and
- Apply a linear transformation to standardize the raw score, so that scores range from 0 to 100.

For each scale at baseline, each post-baseline time point, and the last on-treatment assessment, the derived scores and change in scores from baseline will be summarized using descriptive statistics. The change from baseline for physical function (Q1-5) and role function (Q6-7) at specific timepoints (3 and 6 months) will be compared between the two arms. The function scale at 3 months will be calculated as the average of its score on C2D29 visit and C3D1 visit;

CONFIDENTIAL Page 19 of 29

similarly, the function scale at 6 months will be calculated as the average of its score on C5D29 visit and C6D1 visit.

8.3.3.2. DLOI

DLQI measures the impact of skin symptoms on the QOL of an affected person. This questionnaire has 10 questions, covering the following topics: symptoms, embarrassment, shopping and home care, clothes, social and leisure, sport, work or study, close relationships, sex, and wider treatment consequences. Each question refers to the impact of the skin disease on the patient's life over the previous week. Each question is scored at four levels from "Not at all" (0), through "A little" (1), and "A lot" (2), to "very much" (3), giving a summary score range from 0 (meaning no impact of skin disease on QOL) to 30 (meaning maximum impact on QOL). A difference of four is considered to be clinically significant in inflammatory skin disease.

The total score for the DLQI will be calculated by summing the score of each question per the scoring manual (see http://sites.cardiff.ac.uk/dermatology/quality-of-life/dermatology-quality-of-life-index-dlqi/dlqi-instructions-for-use-and-scoring/). Higher scores are associated with a lower quality of life. The total score will be summarized descriptively using proportions who are moderately impacted (a total score of six to ten points) and severely impacted (a score of eleven or more) at baseline, each post-baseline time point, and the last on-treatment assessment.

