#### 9.8.5.2.4. DLQI

The total score for the DLQI will be calculated by summing the score of each question for both Ex11 ITT and AP ITT separately, per the scoring manual (see <http://sites.cardiff.ac.uk/dermatology/quality-of-life/dermatology-quality-of-life-index-dlqi/dlqi-instructions-for-use-and-scoring/>). Higher scores are associated with a lower the quality of life. The total score will be summarized using descriptive statistics, including proportions who are moderately impacted (a total score of six to ten points) and severely impacted (a score of eleven or more). In addition to the total score, continuous descriptive statistics will also be displayed by section as follows:

Section	Questions Included
Symptoms and Feelings	1,2
Daily Activities	3,4
Leisure	5,6
Work and School	7
Personal Relationships	8,9
Treatment	10

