1. INTRODUCTION

This Statistical Analysis Plan (SAP) describes the detailed methodology for summary and statistical analyses of data from clinical protocol DCC-2618-03-002 (INTRIGUE) based on Amendment 6 of the study protocol, dated 23 October 2020. This document may modify the plans outlined in the protocol and supersedes the previous versions of the SAP and the statistical sections of the protocol.

Populations for analysis, statistical methods, data handling rules, and formats for data presentation are described within this document. The statistical analyses and summary tabulations described in this SAP will provide the basis for the results sections of the Clinical Study Report (CSR) for this trial. Analysis plan of population pharmacokinetics (PK) and exposure-response analysis, pharmacodynamics data, and quality-of-life (QOL) data collected for exploratory objectives will be separately documented.

Any changes to the data analysis methods after the SAP is finalized will be described in the CSR.

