8.3.3.4. EQ-VAS

EQ-VAS is the sixth item of EQ-5D-5L. It records the patient's self-rated health on a vertical visual analogue scale with endpoints labeled "the best health you can imagine" and "the worst health you can imagine." A patient is asked to "mark an X on the scale to indicate how your health is TODAY" and "write the number you marked on the scale in the box below."

EQ-VAS at each post-baseline time point, and the last on-treatment assessment, and change in scores from baseline will be summarized using descriptive statistics. The change in EQ-VAS from baseline at specific timepoints (3 and 6 months) will be compared between the two arms. The EQ-VAS at 3 months will be calculated as the average of its score on C2D29 visit and C3D1 visit; similarly, the EQ-VAS at 6 months will be calculated as the average of its score on C5D29 visit and C6D1 visit.

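### SAP 8.3.3.2 reports the 0–30 DLQI total only as the shares scoring 6–10 and 11 or more, dropping the protocol's score summaries and planning no change from baseline

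*SAP*

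**What the plan says.** SAP 8.3.3.2 sums ten items to a total, "giving a summary score range from 0 (meaning no impact of skin disease on QOL) to 30 (meaning maximum impact on QOL". It then says how that total will be reported: "The total score will be summarized descriptively using proportions who are moderately impacted (a total score of six to ten points) and severely impacted" (11 or more), at baseline, each post-baseline time point and the last on-treatment assessment. The section names no mean, median, spread, change from baseline or section score.

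Protocol 9.8.5.2.4 is broader. It states that "The total score will be summarized using descriptive statistics, including proportions who are moderately impacted", so the proportions are one item among several, and that "continuous descriptive statistics will also be displayed by section as follows", followed by six sections.

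SAP section 1 settles precedence: the SAP "supersedes the previous versions of the SAP and the statistical sections of the protocol".

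Elsewhere in the same SAP, 8.3.3.1 summarises QLQ-C30 scores and their change from baseline and compares physical and role function between arms at 3 and 6 months. SAP 8.3.3.4 does the same for EQ-VAS: "The change in EQ-VAS from baseline at specific timepoints (3 and 6 months) will be compared between the two arms". GP5 (8.3.3.3) is only summarised descriptively.

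**The concern.** Cutting a 31-level score into bands discards the differences within each band.

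- **The lowest band is wide.** A patient who goes from 0 to 5 never appears in either reported share, while one who goes from 5 to 6 counts as newly impacted.
- **The 6–10 band is not monotone.** As skin burden grows, patients enter it from below and leave it at the top, so its share alone can stay flat while scores worsen.
- **No average worsening can be read off.** Without a mean or a change from baseline, the report cannot say by how much skin-related quality of life moved in either arm.

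The DLQI is the trial's only skin-specific quality-of-life instrument, and all three adverse events of special interest are skin lesions. Protocol Table 3 shows that Phase 1 skin events at 150 mg QD were common but mostly Grade 1: rash 26 of 114 (25 Grade 1), hand-foot syndrome 30 (25 Grade 1) and dry skin 12 (11 Grade 1). Toxicity grade is not a DLQI score, but this makes low scores plausible, and that is where the banding loses most.

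**Working it through.** **No plan figure to reproduce.** Neither document gives a DLQI standard deviation, expected proportion, power or test. Everything below rests on assumed distributions.

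**1. Information kept, normal scores.** Take bands <6, 6–10 and ≥11, with continuity-corrected cuts a = (5.5 − mean)/SD and b = (10.5 − mean)/SD. The information kept, relative to the mean, is the sum over bands of (difference in normal density at the band's edges)² / (band probability).

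Worked case, mean 2, SD 3: a = 1.167 and b = 2.833. Band probabilities are 0.878, 0.119 and 0.0023; density differences are 0.202, 0.195 and 0.0072. The sum is 0.0465 + 0.318 + 0.0225 = 0.387.

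| Mean / SD | Three bands | Cut at ≥6 only | Cut at ≥11 only |
|---|---|---|---|
| 2 / 3 | 39% | 38% | 2% |
| 3 / 4 | 59% | 55% | 16% |
| 4 / 4 | 67% | 61% | 23% |
| 5 / 5 | 74% | 63% | 41% |
| 6 / 6 | 77% | 64% | 52% |

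**2. Power, skewed scores (simulation).** Scores are negative binomial capped at 30, two-sided 0.05. Assumed completers are 150 v 130 (ripretinib v sunitinib) near 3 months and 100 v 80 near 6 months. For context, the SAP's PFS medians give 213 × 2^(−t/9) and 213 × 2^(−t/6) progression-free: about 172 and 155 at Day 84, and 125 and 96 at Day 210. With 150 v 130 and SD equal to the mean:

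| Means | Mean of full score | Three bands, trend test | ≥11 alone | 6–10 alone |
|---|---|---|---|---|
| 2 v 3 | 91% | 85% | 34% | 63% |
| 3 v 4.5 | 91% | 86% | 71% | 34% |
| 4 v 6 | 91% | 86% | 78% | 13% |
| 6 v 10 | 99% | 94% | 91% | 5% |

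Over 16 scenarios (these four pairs of means, SD 1.0 or 1.3 times the mean, both sample sizes) the three bands lose about 3 to 14 points against the mean. Simulation error is a point or two.

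**3. Second skewed shape (beta-binomial, 0–30).** With 213 per arm, control mean 3, SD 4 and a difference of 1.5, the other arm's variance is 16 × 4.5/3 = 24. The standard error is √((16 + 24)/213) = 0.433, and 1.5/0.433 − 1.96 = 1.50, so power for the mean is 93%. The ≥6 share, which is the sum of the two reported shares, is 19.7% v 31.6% and has 80% power. The ≥11 share alone has 57% and the 6–10 share alone 37%.

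**4. Non-monotone band.** In the 6 v 10 scenario the 6–10 share is about 23% in both arms, while the ≥11 share is about 18% v 36%.

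**The case against.** The case on the other side is substantial, and most of it limits the size of the point.

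- **Both bands are tabulated together.** The share below 6 follows by subtraction and the ≥6 share by addition, so judging each band alone exaggerates the loss. This stands, and is why the three-band column is the relevant one. It also answers the inference that a large difference could be hidden: where the 6–10 share is flat, the ≥11 share doubles beside it.
- **The gain depends on the shape and the test.** A trend test on the three bands matches or beats a rank test on the full score in nearly every scenario. This stands; the advantage belongs to the mean under the assumed shapes.
- **No DLQI test was planned in either document.** This stands. The power figures only measure information; no planned power is lost.
- **SAP 3.6 prescribes mean, median, SD, minimum and maximum for continuous data.** It might be read as still covering the total. That is arguable, but 8.3.3.2 names its own summary, and 3.6 supplies neither change from baseline nor section scores.
- **The protocol never planned DLQI change from baseline or an arm comparison, and GP5 is equally sparse in the SAP.** True. That part of the fix is an improvement in line with QLQ-C30 and EQ-VAS, not a restoration.
- **The four-point figure is not an analysis criterion.** The SAP says "A difference of four is considered to be clinically significant in inflammatory skin disease", which is background on the instrument and attached to no analysis. It does not show the plan failing a criterion of its own.
- **Other outputs cover skin effects.** Adverse events, AESIs, dermatologic assessments and GP5 do, but none measures skin-related quality of life on a scale.

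**Conclusion.** The point holds as a loss of descriptive and estimation content. The SAP replaces a broader protocol summary with two proportions, drops the six section scores, and plans no change from baseline where two sibling instruments have one.

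The size is moderate and rests on assumption. Read together, the bands keep about 39% to 77% of the information in the mean for normal scores with mean/SD from 2/3 to 6/6, or cost about 3 to 14 power points for skewed scores. The loss is greatest when scores are low.

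A reader might infer that the endpoint loses most of its ability to separate the arms. The documents give no spread or rates that would support this, and the bands keep more than half the information in four of the five normal cases. Nor would a four-point mean difference go unseen: in the beta-binomial case with 100 per arm and control mean 3, SD 4, the ≥11 share is 6.5% v 25.6%, with 96% power.

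The DLQI is outside the testing hierarchy (SAP 8.5), so no primary or key secondary conclusion changes.

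**What to change.** Amend SAP 8.3.3.2 to:

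1. Report n, mean, SD, median, minimum and maximum for the DLQI total and the six section scores, and add change from baseline in the total, by arm, at baseline (scores only), each post-baseline time point and the last on-treatment assessment.
2. Give the between-arm difference in baseline-adjusted mean change with a 95% CI at 3 and 6 months, using the visit averages already defined for the function scales and EQ-VAS. Label it descriptive and outside the hierarchy, and show a bootstrap interval or rank-based check for skew.
3. Keep the 6–10 and ≥11 proportions as a supplement, and also show them cumulatively (≥6 and ≥11).

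A rate of worsening by 4 points or more is optional, since the four-point figure refers to inflammatory skin disease.

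The cost is SAP wording and one or two extra tables. Protocol Table 1 already collects the DLQI at screening, Cycle 1 Day 1 and through treatment, so no new data, visits or patients are needed, and no alpha is used.
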